5.1.5.3. Drug exposure

The date of the first dose will not be imputed. If the date of the last dose is unknown or partially missing, it will be imputed according to the following rules:

- If the date of the last dose is completely or partially missing while the date of death or CRF page for treatment discontinuation is present, the date of the last dose will be imputed as follows:
 - = 31-12-YYYY (if the year YYYY is known, and if YYYY < min (year) [date of treatment discontinuation, date of death])
 - = The last day of the month (if both the year and month are not missing, and if YYYY < min (year) [date of treatment discontinuation, date of death])
 - = The last day of the month (if both the year and month are not missing, and if YYYY = min (year) [date of treatment discontinuation, date of death], and MM < min (month) [date of treatment discontinuation, date of death])
 - = min (date of treatment discontinuation, date of death), other cases.

5.1.5.4. Rules for imputing last survival date and start date of new anti-tumor treatment

5.1.5.4.1. Last survival date

If the investigator is not informed of subject death, the latest date of the following data will be taken as the last survival date:

- All dates of examinations and evaluations of the subjects (tumor response evaluation, blood tests (laboratory, PK), vital signs, physical examination, ECOG PS, pregnancy test, urinalysis, stool routine test, etc.)
- The start and end dates of concomitant medications/concomitant non-drug treatments
- The start and end dates of new anti-tumor treatment after the discontinuation of study treatment
- The start and end dates of AEs
- The date of the last known survival status of the subject on the survival follow-up page

- The start and end dates of study treatment
- Date of withdrawal of informed consent form
- Date of enrollment
- The date on the study discontinuation page (if the reason for discontinuation is "lost to follow-up", the date of lost to follow-up will not be calculated)

5.1.5.4.2. Date of death

If the date of death is completely or partially missing, the last survival date will be used to impute the date of death:

- If the date of death is completely missing, the last survival date + 1 day will be used as the date of death.
- If the day is missing or if both month and day are missing, the date of death = max (last survival date + 1, the date imputed below).
 - Day is missing: 01-MM-YYYY
 - Month and day are missing: 01-01-YYYY

5.1.5.4.3. Start date of new anti-tumor treatment

If the start date of a new anti-tumor treatment is missing, it will be imputed according to the following rules after the end date of study treatment is imputed.

- If the end date of the new anti-tumor treatment is partially missing or not missing, it will be used to derive the start date of the new anti-tumor treatment.
 - If the month and day of the end date of the new anti-tumor treatment are missing while the year is not missing, 31 Dec. will be used as the end date of the new anti-tumor treatment.
 - If only the day of the end date of the new anti-tumor treatment is missing, the last day of the month will be used as the end date of the new anti-tumor treatment.
- If the start date of a new anti-tumor treatment is completely missing or only the year is not missing, it will be derived and imputed according to the following rules:
 - The date of the new anti-tumor treatment is completely missing
The imputed start date = min [max (PD date + 1, date of last dose + 1), end date of the new anti-tumor treatment]
 - Only the year (YYYY) of the start date of the new anti-tumor treatment is not missing

- 1) If $YYYY < \min(\text{year}) [\max(\text{PD date} + 1, \text{date of last dose} + 1), \text{end date of new anti-tumor treatment}]$, the date will be imputed as 31-12-YYYY.
 - 2) In other cases, if $YYYY = \min(\text{year}) [\max(\text{PD date} + 1, \text{date of last dose} + 1), \text{end date of new anti-tumor treatment}]$, the date imputed = $\min [\max(\text{PD date} + 1, \text{date of last dose} + 1), \text{end date of new anti-tumor treatment}]$.
 - 3) In other cases, if $YYYY > \min(\text{year}) [\max(\text{PD date} + 1, \text{date of last dose} + 1), \text{end date of new anti-tumor treatment}]$, the date imputed = 01-01-YYYY.
- The year (YYYY) and month (MM) of the start date of new anti-tumor treatment are not missing
 - If $YYYY = \min(\text{year}) [\max(\text{PD date} + 1, \text{date of last dose} + 1), \text{end date of new anti-tumor treatment}]$, and if $MM < \min(\text{month}) [\max(\text{PD date} + 1, \text{date of last dose} + 1), \text{end date of new anti-tumor treatment}]$, the date will be imputed with the last day of MM.
 - In other cases, if $YYYY = \min(\text{year}) [\max(\text{PD date} + 1, \text{date of last dose} + 1), \text{end date of new anti-tumor treatment}]$, and $MM = \min(\text{month}) [\max(\text{PD date} + 1, \text{date of last dose} + 1), \text{end date of new anti-tumor treatment}]$, then the date imputed = $\min [\max(\text{PD date} + 1, \text{date of last dose} + 1), \text{end date of new anti-tumor treatment}]$.
 - In other cases, if $YYYY = \min(\text{year}) [\max(\text{PD date} + 1, \text{date of last dose} + 1), \text{end date of new anti-tumor treatment}]$, and $MM > \min(\text{month}) [\max(\text{PD date} + 1, \text{date of last dose} + 1), \text{end date of new anti-tumor treatment}]$, then the date imputed = 01-MM-YYYY.
 - In other cases, if $YYYY < \min(\text{year}) [\max(\text{PD date} + 1, \text{date of last dose} + 1), \text{end date of new anti-tumor treatment}]$, the day imputed will be the last day of MM.
 - In other cases, if $YYYY > \min(\text{year}) [\max(\text{PD date} + 1, \text{date of last dose} + 1), \text{end date of new anti-tumor treatment}]$, then the date imputed = 01-MM-YYYY.

5.2. Study Subjects

5.2.1. Disposition of subjects

The number of screened subjects, number of enrolled subjects, number and percentage of treated subjects, number and percentage of subjects in analysis sets (including full analysis set, evaluable analysis set, per-protocol set, safety set, and DLT analysis set), number of subjects who discontinue the study/treatment, and number and percentage of corresponding subjects to the reasons for discontinuation will be summarized.

5.2.2. Demographics

The age, gender, ethnicity, height, weight, body mass index BMI (kg/m²), vital capacity, maximal mid-expiratory flow, peak expiratory flow, forced expiratory volume in 1 second, diffusing capacity for carbon monoxide, oxygen saturation, ECOG PS, smoking history (yes, no), and cigarettes used will be summarized by group using descriptive statistics.

The BMI calculation formula is: $\text{BMI (kg/m}^2\text{)} = \text{baseline weight (kg)} / \text{baseline body height (m}^2\text{)}$.

5.2.3. Tumor diagnosis

The following tumor indicators will be summarized by group using descriptive statistics: histological classification, presence of metastases, number of organs involved in metastasis (≤ 2 , > 2), pathological grade, clinical stage, EGFR, ALK fusion gene, course of disease (years), etc. A detailed listing of subjects for tumor diagnosis will be provided.

The course of disease (years) is defined as the period from the date of initial pathological diagnosis to the date before the first dose. The calculation formula is: $(\text{date of first dose} - \text{date of initial pathological diagnosis} + 1) / 365.25$.

5.2.4. Medical history

A detailed listing of medical history will be provided.

5.2.5. Tumor treatment history

Tumor treatment history mainly includes history of tumor surgery, chemotherapy, targeted therapy, radiotherapy, and other tumor treatments.

For tumor treatment history, the following descriptive statistics are provided:

- Number and percentage of subjects who have previously received any of the above tumor treatments;
- Number and percentage of subjects who have previously received tumor surgery, and number and percentage of subjects by surgery nature;
- Number and percentage of subjects who have received chemotherapy, and number and percentage of subjects by treatment mode;
- Number and percentage of subjects who have received targeted therapy, and number and percentage of subjects by treatment mode and regimens;
- Number and percentage of subjects who have received radiotherapy;
- Number and percentage of subjects who have received other tumor treatments, and number and percentage of subjects by treatment type.

In addition, a detailed listing of subjects will be provided.

5.2.6. Prior therapy and concomitant medication

All prior medications, concomitant medications, and concomitant non-drug treatments will be listed. The information of anti-tumor treatments (including chemotherapy, targeted therapy, radiotherapy, surgery, and others) used after withdrawal due to PD will be summarized and listed. Subsequent anti-tumor treatment refers to other anti-tumor treatment after the last dose.

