5.3 Subject's Withdrawal

5.3.1 Criteria for withdrawal/treatment discontinuation

1. The subject withdraws informed consent and requests to withdraw from the study;
2. Imaging examinations show progressive disease;

Upon the first discovery of progressive disease by imaging examinations, it must be confirmed after 4 weeks (except for rapid progression and significant clinical progression);

If a subject shows local progression (1 to 4 lesions show progress) but the clinical symptoms are stable, the treatment can be continued according to the judgment of the investigator until imaging examinations show progressive disease again.

Definition of clinically stable: a. no clinically significant symptoms or changes in laboratory tests; b. no changes in the performance status score (deterioration); and c. non-tumor rapid progression and tumor progression not involving major organs/sites (e.g., spinal cord compression).

3. Treated by SHR-1210 for 2 years (no progressive disease as shown by imaging);
4. Subjects with intolerable toxicity;
5. Subjects with poor compliance;
6. Subjects lost to follow-ups or show positive blood HCG results;
7. Other reasons for which the investigator considers withdrawal as necessary.

Note: Subjects with radiologically confirmed PD may continue the study drug after providing informed consent for continuation after PD, if they are judged able to benefit from the study drug by the investigator. The treatment may continue until another radiographic PD or they can no longer benefit from the treatment. Subjects who continue the medication after PD will undergo periodic visits and efficacy evaluations according to the visit procedures specified in the protocol.

Subjects who agree to continue the treatment after PD should be fully informed of possible alternative treatments, potential risks of continuation, etc.

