5.3.2 Handling of withdrawn subjects

The efficacy and safety investigations to be completed upon study withdrawal as specified in the protocol must be completed as much as possible. In addition, the safety follow-up should be completed along with fully collected AEs and their outcomes. The survival follow-up should be completed to record subsequent treatment regimens and the survival status of the subjects. The investigator can recommend or provide new or alternative treatments to a subject based on the condition of the subject. Patients showing no progressive disease need to be continuously followed-up for imaging evaluation until the patients begin a new treatment or show progressive disease

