- [23] Return and dispensation of apatinib. Apatinib will be dispensed on Day 1 of Cycle 1 (dispensed to subjects in the drug expansion study from Day 22 of Cycle 1). From Day 1 of Cycle 2, the return and dispensation of apatinib will be performed on Day 1 of each cycle. The remaining drugs will be returned first to verify the dose actually taken before new study drugs are dispensed.
- [24] Imaging test: including CT or MRI of the chest, abdomen, and brain. The baseline tumor assessment during the screening period can be extended to up to 3 weeks before treatment. Qualified CT/MRI scan results obtained before signing the informed consent can be used for tumor assessment during the screening period. Bone scan should be performed upon clinically suspected bone metastasis. Absence of cerebral hemorrhage should be confirmed within 21 days before randomization for subjects with stable brain metastases.
- During the treatment period, imaging examinations should be performed under the same conditions as those at baseline (layer thickness of the scan, use of contrast agent, etc.), and the lesions found at baseline should be checked every 2 cycles in the first 6 cycles of the treatment (bone scan shall be performed in the case of suspected bone progression or for CR confirmation). After 6 cycles, imaging examinations can be performed every 3 weeks as appropriate and can be performed upon the discovery of suspected new lesions. Initial assessment of PR/CR must be confirmed after 4 weeks; initial assessment of PD must be confirmed after 4 to 6 weeks (except for significant changes in the subjects' symptoms or rapid tumor progression).
- The window period for imaging examination schedule is ± 7 days. Unscheduled imaging examinations can be performed when progressive disease is suspected (such as worsening of symptoms).
- [25] A tumor assessment is required at the end of treatment for subjects who discontinue study treatment for reasons other than radiographic PD, if not performed within 4 weeks prior to study completion. Also, treatment efficacy will be followed up once every 3 months after study completion, until documentation of confirmed PD or start of a new anti-tumor treatment.
- [26] Survival follow-up: After the study treatment is discontinued, the survival status and subsequent anti-tumor treatment can be collected through clinical or telephone follow-ups every 2 months until death.

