4.1.6. Progression-free survival (PFS)

Progression-free survival (PFS): defined as the period of time from the date of first dose to the date of the first documented tumor progression (as per RECIST v1.1, regardless of whether treatment is continued) or death of any cause (whichever occurs first).

Censoring rules:

- If there is no baseline tumor measurement or there is baseline tumor evaluation but with missing tumor evaluation after baseline, censoring will be based on the date of first dose.
- If there is no radiographic PD or death before the start of any new anti-tumor treatment, censoring will be based on the date of the last effective efficacy evaluation prior to the new anti-tumor treatment.
- If the subject does not have radiographic PD or die before the end of study or dropout, and has not received new anti-tumor treatment before the end of study or dropout, censoring will be based on the date of the last effective efficacy evaluation.
- For death or PD occurring after two or more missed planned visits, censoring will be performed based on the date of the last effective efficacy evaluation prior to death or PD.

4.1.7. 12-month overall survival rate (12-OS%)

The 12-month overall survival rate refers to the probability of being alive at Month 12 from the first dose of study treatment, and is assessed by Kaplan-Meier method.

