4.1.8. Overall survival (OS)

Overall survival (OS): defined as the time from the date of first dose to death due to any cause.

Censoring rules are as follows:

- If there is no death or dropout by the end of study, the censoring date will be the last date when the survival status (alive) is obtained.

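### SAP 5.2.6 limits the only planned summary and listing of later anti-tumor treatment to withdrawals for progression, against its own definition and the protocol's wider data collection

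*SAP*

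**What the plan says.** SAP 5.2.6 contains one sentence that plans an output for later therapy. Anti-tumor treatments (chemotherapy, targeted therapy, radiotherapy, surgery and others) "used after withdrawal due to PD will be summarized and listed". The sentence after it is a definition without a progression condition: "Subsequent anti-tumor treatment refers to other anti-tumor treatment after the last dose".

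The protocol collects the information more widely. Section 7.4 says that, once study treatment is discontinued, "the survival status and subsequent anti-tumor treatment can be collected through clinical or telephone follow-ups every 2 months until death"; schedule note [26] says the same. Section 5.3.2, on withdrawn subjects, says: "The survival follow-up should be completed to record subsequent treatment regimens and the survival status of the subjects". Neither passage depends on why the subject stopped.

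Protocol 5.3.1 lists progression as one of several reasons for stopping. Others are withdrawal of consent, completion of 2 years of SHR-1210, "Subjects with intolerable toxicity", poor compliance, loss to follow-up and investigator judgment.

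New therapy also enters the endpoint definitions. SAP 4.1.4 (DoR) and 4.1.6 (PFS) censor at the last evaluation before new therapy under the condition "If there is no radiographic PD or death before the start of any new anti-tumor treatment". OS in SAP 4.1.8 has no such rule. For a subject not known to have died, "the censoring date will be the last date when the survival status (alive) is obtained".

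**The concern.** Someone programming the table from the sentence that specifies the output would keep only subjects withdrawn for progression. A subject who stopped for toxicity and then started another drug would appear in neither the summary nor the listing, although the case report form holds the data.

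This matters in two ways. First, the study is uncontrolled and OS runs on through later therapy, so readers will set OS and 12-month survival beside the reported rate of later treatment. A rate that leaves out part of the population is too low for that use. Second, new therapy before progression affects several analyses. It censors PFS and DoR, closes the assessment window for ORR and BOR (SAP 4.1.1, 4.1.2) and affects membership of the evaluable set (SAP 5.1.1). SAP 5.3.4 and 5.3.6 plan no tabulation of censoring reasons, so the later-therapy listing is where a reader would look to see how often this happened and what was given.

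**Working it through.** There is no stated figure to reproduce. The check compares the scope of the relevant sections and then writes the possible shortfall as a formula.

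**Scope, section by section**

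| Place | What it covers | Limited to PD? |
|---|---|---|
| SAP 5.2.6, output sentence | Summary and listing of later therapy | Yes |
| SAP 5.2.6, definition | Anti-tumor treatment after the last dose | No |
| SAP 5.1.5.4.3 | Imputing missing start dates of new therapy | No |
| SAP 5.2.1 | Counts by reason for discontinuation, without later therapy | No |
| Protocol 5.3.2, 7.4, schedule note [26] | Collection of later therapy | No |

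Only the reporting sentence is narrow.

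**Are the omitted subjects the ones censored at new therapy?** Only in part.

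- Stopped for toxicity, no radiographic PD, then new therapy: omitted from the table, and PFS censored. DoR is also censored if the subject had responded.
- Stopped for toxicity, with radiographic PD found in the 3-monthly imaging (protocol 7.3, note [25]) before new therapy: omitted from the table, but PFS is an event.
- Treated beyond PD, then stopped for toxicity: omitted, but PFS is already an event. Protocol 5.3.1 allows this, since such subjects "may continue the study drug after providing informed consent for continuation after PD".
- Withdrawn for clinical progression without imaging evidence (protocol 8.2.2 counts this as PD), then new therapy: in the table, yet PFS is censored.

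The groups overlap without coinciding.

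**Size of the shortfall**

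Among all subjects who stop study treatment, let s be the share stopping for non-PD reasons, u1 the uptake of later therapy after PD, and u2 the uptake after other reasons.

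- Rate shown by a PD-only table: (1 − s) × u1
- Full rate: (1 − s) × u1 + s × u2
- Shortfall: s × u2

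The documents give none of s, u1 or u2. Assumed for illustration: s = 10%, 20% or 30%; u1 = 50%; u2 = 0%, 30% or 50%.

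| s | PD-only rate | Full rate (gap), u2 = 50% | Full rate (gap), u2 = 30% | Full rate (gap), u2 = 0% |
|---|---|---|---|---|
| 10% | 45% | 50% (5 points) | 48% (3 points) | 45% (0) |
| 20% | 40% | 50% (10 points) | 46% (6 points) | 40% (0) |
| 30% | 35% | 50% (15 points) | 44% (9 points) | 35% (0) |

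For example, with s = 20% and u2 = 30%, the gap is 0.20 × 0.30 = 6 points. It does not depend on u1, and it is zero if no subject who stopped for a non-PD reason starts later therapy.

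**The case against.** The strongest reply is that the definition in 5.2.6 already sets the scope. It follows the output sentence directly, has no PD condition, and has no evident use except to describe this output. On that reading *due to PD* is loose drafting and nobody is left out. This has force: the author may well have intended the wider table. But a definition does not order an output, and the only sentence that does carries the limit. The two need to be reconciled whichever was meant.

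It can also be said that SAP 5.2.1 already tabulates reasons for discontinuation, so a reader can see how many stopped for non-PD reasons and why. That stands. What is missing is the therapy those subjects went on to receive.

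Finally, no estimate depends on this table. OS, PFS, DoR and ORR are computed the same way under either wording, and SAP section 3 plans no formal hypothesis. That stands too.

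Two stronger readings are tempting, and the documents support neither.

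- A reader might infer that the omitted subjects are exactly those censored at new therapy. The cases under the check show that they are not.
- A reader might take the 20% dropout rate in SAP 2.3 as the non-PD share, assume that half to all of those subjects start new therapy, and arrive at an understatement of 10 to 20 points (0.20 × 0.50 to 0.20 × 1.00). The 20% is a sample-size allowance (62 / 0.8 = 77.5, rounded up to 78). It is not described as a rate of stopping for non-PD reasons, and none is stated for Cohort 4. The uptake range has no source in the documents and excludes low or zero uptake.

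**Conclusion.** The point holds as a conflict of scope in one SAP paragraph that, followed literally, gives an incomplete report of later therapy. The shortfall in the reported rate is s × u2. The documents supply neither quantity, so its size is unknown and may be zero; the range of 0 to 15 percentage points rests wholly on the assumed inputs. Many subjects censored for PFS or DoR at new therapy would probably be among those left out, because that rule requires no earlier radiographic PD, but the overlap is partial. The fault concerns reporting and interpretation only. It biases no efficacy estimate and is a minor improvement to make before database lock.

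**What to change.** In SAP 5.2.6, delete *due to PD* and align the output sentence with the definition that follows it. Suggested wording: all anti-tumor treatment started after the last dose of study treatment, whatever the reason for discontinuation, will be summarized for the FAS by population/cohort and listed.

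Optional additions are the reason for discontinuation and a flag showing whether the new therapy began before radiographic PD. These would let a reader connect the listing to the PFS and DoR censoring, but they are not needed to resolve the conflict.

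The cost is one edited sentence and a wider selection in a table already planned. No new data are required, because the protocol already collects later therapy from every subject who stops and the SAP already derives its start dates.
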